## 8.3 RISK MANAGEMENT AND SAFETY

If a participant becomes ill during the study, or in the event that they suffer an injury as a result of the study, participants will be advised to contact the study doctor. The study doctor will arrange for appropriate treatment.

Participants will be made aware there is a risk of embarrassment and discomfort arising from the disclosure of personal and sensitive information. The study site will ensure that all participants' personal information is de-identified in all study records and in any future publication of study results.

### 8.3.1 DEFINITIONS

An adverse event (AE) is any untoward, undesired, or unplanned event in the form of signs, symptoms, disease, or laboratory or physiologic observations occurring in a person given an investigational product (where applicable). The event does not need to be causally related to the investigational product (where applicable). An AE includes, but is not limited to, the following:

- Any clinically significant worsening of pre-existing condition
- An AE occurring from overdose of an investigational event (where applicable), whether accidental or intentional.
- An AE occurring from abuse (i.e., use for nonclinical reasons) of an investigational product/procedure (where applicable)

A serious adverse event (SAE) is an AE that:

- Results in death
- A life-threatening AE: An AE is considered 'life-threatening', if in the view of the investigator, it places the patient at an immediate risk of death.
- Requires inpatient hospitalization or an extension of an existing hospitalization
- Results in a persistent or significant disability or incapacity
- Results in a congenital anomaly or birth defect
- Results in an important medical event.

Important medical events are AE's that may not result in death, be life-threatening, or require hospitalization may be considered SAEs when, based upon appropriate medical judgment, they may jeopardize the patient and may require medical or surgical intervention to prevent one of the outcomes listed in this definition. Examples of such medical events include allergic bronchospasm requiring intensive treatment in an emergency room or at home, blood dyscrasias or convulsions that do not result in hospitalization, or the development of drug dependency or drug abuse.

Hospitalization is the official admission to a recognized hospital. Hospitalization or prolongation of a hospitalization constitutes a criterion for an AE to be serious; however, it is not in itself considered an SAE. In the absence of an AE, any hospitalization or prolongation of a hospitalization should not be recorded by the investigator as a serious adverse event.

### 8.3.2 ADVERSE EVENT AND SERIOUS ADVERSE EVENT RECORDING AND REPORTING

Determination of AEs will be based upon the signs and symptoms identified during the physical examination and on clinical evaluation of the participant. The signs and symptoms will be recorded using standard medical terminology. Any identified AEs and SAEs will be reported from the signing of the informed consent form to the end of Week 24 (end of study). The investigator must instruct the patient to report any AEs and SAEs during this time period.

The investigator will also comply with the applicable regulatory requirement(s) related to the reporting of unexpected serious adverse events to the regulatory and the Human Research Ethics Committee (HREC).

### 8.3.3 ADVERSE EVENT FOLLOW UP

All AEs will be followed through the end of the study and be recorded as “continuing” if not resolved at the last study visit. All SAEs will be followed to resolution or stabilization.

### 8.3.4 DEFINITION OF SCREENING FAILURES

A “screening failure” is a participant from whom informed consent is obtained and documented in writing (that is, the subject or legally authorized representative as required by local law and regulations, and the participant’s carer has signed an informed consent form), but who has not commenced receiving the study medication.

### 8.3.5 DEFINITION OF COMPLETED PARTICIPANTS

A participant will be deemed to have completed the study once the participant had follicular unit extraction or had topical clindamycin and followed up as part of standard routine care up to week 24.

## 8.4 REPLACEMENTS

There will be no replacements if participants withdraw.

# 9. STATISTICAL METHODS

## 9.1 SAMPLE SIZE ESTIMATION & JUSTIFICATION

Given that this is a pilot study assessing the effectiveness of FUE for HS management, we have decided 24 participants is required as a pilot. The result of this study will be used to inform sample size calculations for future studies as well as account for 20% rate of lost to follow-up.

## 9.2 POWER CALCULATIONS

This pilot study uses 12 participants in each group (intervention vs controlled) and results from this will allow us to calculate the sample size required for statistical power in future clinical studies.

## 9.3 STATISTICAL METHODS TO BE UNDERTAKEN

Abscess and nodule counts will be recorded and then compared at the study visits up to week 24. This will be done using the paired t test.

Paired t test will also be used to compare changes in HS-PGA, IHS4 and HiSCR scores between the treated and control sites.

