Statistical Methods:	Paired t test to assess change in Hurley stage, Hidradenitis Suppurative-Physician's Global assessment score, numerical pain score, IHS4 score, HiSCR score.
Subgroups:	

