## 6. STUDY OBJECTIVES

### 6.1 HYPOTHESIS

Participants receiving FUE will have lower scores for HiSCR, HS-PGA, IHS4, NRS30 compared to those receiving standard topical resorcinol/clindamycin.

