#### Secondary objective.

2. Comparing scores of HS severity assessments between intervention and control group at week 6, 12 and 24 after follicular unit extraction.
3. Comparing scores of HS severity assessments before and after follicular unit extraction on the treated site at week 6, 12 and 24 after follicular unit extraction.
4. To compare the number of disease flares between intervention and control group over 24 weeks.
5. To determine if specimens contain HFs, sebaceous glands, apocrine glands and eccrine glands on histopathology.

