### 6.3 OUTCOME MEASURES

1. Hidradenitis suppurativa clinical response score (HiSCR)
2. Hidradenitis suppurativa – Physician’s global assessment (HS-PGA)
3. International Hidradenitis Suppurativa Severity Score System (IHS4)
4. Pain score (NRS30)
5. Number of abscesses and nodule counts at each visit
6. Number of flare ups as well as location of flare ups

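### Section 9.3 gives NRS30 pain, and on its natural reading the lesion counts, no comparison with the control arm, although the hypothesis claims one for pain

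*Protocol*

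**What the plan says.** Section 9.3 of the protocol contains two analysis statements.

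- On lesion counts: "Abscess and nodule counts will be recorded and then compared at the study visits up to week 24", followed by "This will be done using the paired t test". No comparator is named.
- On three scores: "Paired t test will also be used to compare changes in HS-PGA, IHS4 and HiSCR scores between the treated and control sites". Neither lesion counts nor pain is in that list, and NRS30 is not mentioned anywhere in 9.3.

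The only analysis named for pain is in the synopsis, under Statistical Methods, where a paired test is to be used as a "test to assess change in Hurley stage, Hidradenitis Suppurative-Physician's Global assessment score, numerical pain score, IHS4 score, HiSCR score". That line does not mention the control arm.

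The questions are set elsewhere. The hypothesis in 6.1 reads "Participants receiving FUE will have lower scores for HiSCR, HS-PGA, IHS4, NRS30 compared to those receiving standard topical resorcinol/clindamycin". Secondary objective 2 in section 6.2 is "Comparing scores of HS severity assessments between intervention and control group at week 6, 12 and 24 after follicular unit extraction". Objective 3, directly after it, is a before-and-after comparison on the treated site at the same weeks. Section 6.3 lists pain (NRS30) as outcome 4 and "Number of abscesses and nodule counts at each visit" as outcome 5. Section 6.4.1.8, on severity assessment, describes both. Sections 6.6 and 9.2 make the arms 12 and 12 different randomised people.

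**The concern.** The hypothesis on pain is a statement about one randomised group against another. The analysis fixed for pain looks only at change, and a paired test of change within an arm uses no control data. The same holds for lesion counts if they are compared only from visit to visit.

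Change over 24 weeks need not come from FUE. Section 5.2 describes recurrent lesions, and section 6.4.1.6 allows topical, oral, intralesional and surgical management of flares as routine care. The trial is open-label and pain is self-rated. If both arms improve for such reasons, a significant before/after result in the FUE arm says nothing about FUE against control. The trial would have randomised a control group and then not used it for an outcome named in its own hypothesis.

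**Working it through.** **1. Which outcomes get a comparison with control?**

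| Outcome | In hypothesis 6.1 | Treated v control in 9.3 | Other stated analysis |
|---|---|---|---|
| HiSCR, HS-PGA, IHS4 | yes | yes (paired t test) | synopsis, paired test of change |
| NRS30 pain | yes | no | synopsis, paired test of change |
| Abscess and nodule counts | no | no | 9.3, paired test across visits |

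For pain, the stated question and the stated method do not match. For counts, the mismatch is with secondary objective 2 only, and only if counts are taken as part of the severity assessments. Section 6.4.1.8 supports that reading but does not state it outright.

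**2. The plan's own figure.** There is no power calculation to reproduce. The total of 24 is a chosen pilot size, and 12 + 12 = 24 agrees with section 9.2.

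**3. What a within-arm paired test does under shared change.** From the protocol: n = 12 per arm, and the 20% loss mentioned in 9.1, giving 12 × 0.8 = 9.6, or about 10 per arm. Assumed, because the protocol gives neither: two-sided alpha 0.05, and a shared improvement of d SDs of change in both arms with no FUE effect. Change scores are taken as normal.

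The paired t statistic in the FUE arm is then noncentral t with n − 1 degrees of freedom and noncentrality d√n. The chance of significance is P(|T| > t₀.₉₇₅,ₙ₋₁). The critical value is 2.201 at n = 12 and 2.262 at n = 10.

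| d | d√12 | significant, n = 12 | significant, n = 10 |
|---|---|---|---|
| 0.1 | 0.346 | 6.2% | 5.9% |
| 0.2 | 0.693 | 9.7% | 8.8% |
| 0.3 | 1.039 | 15.8% | 13.6% |
| 0.5 | 1.732 | 35.3% | 29.3% |
| 0.8 | 2.771 | 71.4% | 61.6% |

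**4. The between-arm test.** The shared shift cancels in the difference between arms, so a two-sample t test on change keeps its 5% level. Simulation (100,000 trials per setting, d from 0.3 to 1.0, 10 or 12 per arm) gave 4.9% to 5.0%.

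**5. The price in power.** For a 0.8 SD effect at 12 per arm, the two-sample noncentrality is 0.8 × √(12/2) = 1.960 with 22 degrees of freedom (critical value 2.074), giving power 0.466. The paired test reaches 0.714 for a change of the same size, but it is testing total change and not the difference from control.

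**The case against.** The strongest reply is that the paired test has a legitimate job. Secondary objective 3 asks for a before/after comparison on the treated site, and the synopsis states its primary objective as change through follow-up. This stands, and the fix must not remove that analysis. It does not supply the between-arm test for pain.

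A second reply is that the between-arm intent for pain is stated in 6.1 and could be carried out under an analysis plan not seen here. Part of this stands: mere silence would be no finding. But the protocol is not silent. It names a test for pain, and it names which outcomes are compared with control.

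Several stronger readings are tempting and are not supported:

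- *Counts contradict the hypothesis.* They do not; 6.1 does not name them. HiSCR, IHS4 and HS-PGA are all computed from lesion counts and are assigned a treated-versus-control comparison, so improvement shared by both arms could show there. Pain has no such cover.
- *Counts are certainly tested only across visits.* The wording does not strictly exclude an arm comparison. Across visits is the natural reading, because the next sentence adds a comparator for three scores only.
- *Both arms will be pooled.* Nothing in the protocol says so.
- *Shared improvement will be reported as an FUE effect.* No passage says this; it is a risk. Stabilising medication under 6.4.1.6 is given before the procedure and could lower the week 0 value, making later worsening plausible too.
- *Any realistic drift grossly inflates false positives.* At 0.1 or 0.2 SD the rate is only about 6% or 10%.

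**Conclusion.** The point holds, chiefly for NRS30. The protocol claims a between-arm difference in pain and fixes an analysis that cannot test it. For abscess and nodule counts it is a lesser gap, resting on the natural reading of 9.3 and on counts belonging to the severity assessments of objective 2.

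The size depends wholly on the assumed shared improvement, for which the protocol gives no figure: from close to nominal at 0.1 SD to about 71% at 0.8 SD with 12 in the FUE arm. What does not depend on that assumption is that a within-arm test gives no estimate of the difference from control. The protocol should be amended, but the change is modest and uses data already planned in both arms at weeks 0, 6, 12 and 24.

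**What to change.** In 9.3, and to match in the synopsis Statistical Methods line, state in substance:

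> NRS30 pain and abscess and nodule count at weeks 6, 12 and 24 will be compared between the randomised arms by analysis of covariance adjusted for the week 0 value, and reported as a between-arm difference with 95% confidence interval. Paired before/after analyses within the FUE arm address secondary objective 3 and are not evidence of an effect against control.

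Do not simply add the two outcomes to the existing treated-versus-control sentence. It prescribes a paired t test, which is not valid between 12 and 12 different participants, and both outcomes would inherit that error.

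The cost is wording only; no visit or measurement is added. The downside is precision: about 47% power for a 0.8 SD difference by an unadjusted comparison of change at 12 per arm, against 71% for the paired test of change. That is acceptable in a pilot that states no power and is meant to inform the sample size of later studies, for which a between-arm estimate is the useful quantity.

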### 6.4 STUDY TYPE & DESIGN & SCHEDULE

#### 6.4.1 STUDY ASSESSMENTS

##### 6.4.1.1 SUBJECT DEMOGRAPHICS

Demographic and baseline characteristics to be collected on participants include: Date of birth, gender, ethnicity and child-bearing potential (for females only).

20 participants will be recruited and divided into intervention and controlled group in a 1:1 ratio.

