#### 6.4.1.6 MANAGEMENT OF FLAREUPS

Participants may be given medications to prevent flares to stabilize the condition prior to follicular unit extraction. This may be resorcinol 15% cream and/or oral antibiotics such as doxycycline 100mg. Often, flareups may need surgical management or intralesional corticosteroids. These are given as part of standard routine care to minimize flare-ups for the hidradenitis suppurativa and alleviate symptoms for patients and is part of management guidelines.

Participants may be given a sheet to document their flareups (Appendix 3). Participants may take photos of the flareups on their phone to show to the investigator but this is optional only. Investigators will not be collecting photos taken by participants.

Participants are divided into the intervention group and control group. The control group will be managed with topical clindamycin. A staff member of Sinclair Dermatology not involved in this study will randomise participants into the intervention and controlled group using the program from [www.randomizer.org](http://www.randomizer.org) in a 1:1 stratification ratio. The treatment group will be treated with follicular unit extraction. Due to the study design (the intervention being surgical and the controlled group being a topical application), investigators and participants are unable to be blinded as to which participants will be in the treatment or control group. As there will be 24 participants in this study, numbers 1-24 will be randomly allocated to either control or treatment group using [randomizer.org](http://randomizer.org) prior to recruitment of the study. Participants will then be allocated a number in the order in which they are recruited in the study and subsequently will be placed in the group that the number has been randomised into.

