#### 6.4.1.7 FOLLICULAR UNIT EXTRACTION AND HISTOPATHOLOGY

Participants will be taken to the procedure room. Local anaesthesia will be injected into diseased hair-bearing area on both sides of either the axillae or groin. FUE will be performed by the investigator (who is experienced in FUE) using 0.8/0.9/1.0 mm Ertip® punch. The extracted hair follicular unit samples will have histopathological analysis to confirm complete removal of hair follicles, sebaceous glands, apocrine glands and eccrine glands. These samples are not kept for future studies and will be discarded once complete removal of the pilosebaceous units are confirmed. Participants will not be charged for samples being analysed to confirm complete removal of the pilosebaceous units.

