## 6.6 RANDOMISATION

A staff member of Sinclair Dermatology not involved in this study will randomise participants into the intervention and controlled group using the program from [www.randomizer.org](http://www.randomizer.org) in a 1:1 stratification ratio. The treatment group will be treated with follicular unit extraction. Due to the study design, investigators and participants are unable to be blinded as to which participants will be in the treatment or control group. As there will be 24 participants in this study, numbers 1-24 will be randomly allocated to either control or treatment group using [randomizer.org](http://randomizer.org) prior to recruitment of the study. Participants will then be allocated a number in the order in which they are recruited in the study and subsequently will be placed in the group that the number has been randomised into.

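### Section 9.3 compares FUE with control by a paired t test, but the trial has two independent randomised groups and no treated/control pairs

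*Protocol*

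**What the plan says.** Section 9.3 names one test for the comparison of FUE with control: "Paired t test will also be used to compare changes in HS-PGA, IHS4 and HiSCR scores between the treated and control sites". The paragraph before it applies a paired t test to lesion counts over time: "Abscess and nodule counts will be recorded and then compared at the study visits up to week 24". The synopsis also lists only a paired t test, there to assess change in the scores.

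The design sections describe something other than paired sites:

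- Section 6.6 randomises people: "numbers 1-24 will be randomly allocated to either control or treatment group". Numbers are then given out in order of recruitment, and no matching is described.
- Section 9.2 gives the arm size: "This pilot study uses 12 participants in each group (intervention vs controlled".
- Section 6.4.1.7 has the FUE group treated bilaterally: "Local anaesthesia will be injected into diseased hair-bearing area on both sides of either the axillae or groin". Sections 5.1 and 6.7 agree.
- Section 6.4.1.6 describes the comparator as a separate group: "The control group will be managed with topical clindamycin".

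The first of the secondary objectives in Section 6.2 is a between-group question: "Comparing scores of HS severity assessments between intervention and control group at week 6, 12 and 24 after follicular unit extraction". So is the hypothesis in Section 6.1.

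**The concern.** A paired t test needs each treated observation to be tied to a particular control observation, in the same person or a matched one. The reference to sites in 9.3 suits a split-body trial, in which one side is treated and the other left as control. Here an FUE participant has no contralateral control site, and a control participant has no FUE-treated site. The only natural pairs are before and after in the same person, and those do not compare the arms.

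What is at stake is the only stated test of the Section 6.1 hypothesis. An analyst who follows 9.3 literally must invent a pairing, and the standard error, confidence interval and p-value then rest on that invention. The sentence also puts HiSCR through a t test, although Section 6.4.1.8 defines it as a response that is either met or not met relative to baseline.

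**Working it through.** The protocol has no power figure to reproduce: it gives no alpha, power, effect size or SD. Two-sided 5% is assumed below.

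**Inputs from the protocol.** 12 per group (9.2); 20% loss to follow-up (the figure mentioned in 9.1); no replacement (8.4).

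**1. Is there a pair?** Individual randomisation (6.6), bilateral FUE (6.4.1.7, 6.7) and a separate topical group (6.4.1.6) leave no participant with both conditions. No matching is described, so any pairing across arms is arbitrary.

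**2. Does the pairing matter?** In one simulated 12-versus-12 data set with an observed mean difference of 1.24, the unpaired p was 0.00009. Over 20,000 random pairings of the same data, the paired p ran from 0.000002 to 0.005. Every pairing was significant in that example, but p varied more than a thousandfold with the mean difference unchanged.

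**3. Type I error.** In 100,000 simulated null trials, pairing unrelated to outcome gave 5.0%. Pairing by rank of outcome gave about 51%. The first shows that a neutral pairing is not biased; the second shows why an undefined pairing is unsafe.

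**4. Cost with no loss.**
- Unpaired df = 12 + 12 − 2 = 22, critical t = 2.074.
- Paired df = 12 − 1 = 11, critical t = 2.201.
- Ratio 2.201 / 2.074 = 1.06, so the interval is about 6% wider.
- Power for a true difference of 1.0 SD (assumed) falls from 0.65 to 0.61.

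**5. Cost with 20% independent loss in each arm.**
- Probability of equal numbers of completers: the sum over k of [Binomial(12, 0.8) at k]² = 0.20. In the other 80% of trials participants must be dropped before a paired test can run.
- Pairs fixed beforehand, for example by recruitment order: expected complete pairs 12 × 0.8² = 7.68, df 6.68, critical t = 2.388.
- Unpaired: expected 12 × 0.8 = 9.6 per arm, df 2 × 9.6 − 2 = 17.2, critical t = 2.108.
- Ratio of interval widths: (2.388 / 2.108) × √(9.6 / 7.68) = 1.133 × 1.118 = 1.27, about 27% wider.

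The 27% uses expected counts and applies to pairs fixed before the losses. Re-pairing completers afterwards would discard fewer people, but it would make the pairing a choice taken after outcomes are known.

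**6. Scale of the outcomes.** IHS4 is a weighted lesion count. HS-PGA is an ordered category from 0 to 5 (Appendix 1). HiSCR is yes/no and defined against baseline, so it has no Week 0 value from which to change.

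**The case against.** The strongest reply is that this is a small pilot with no powered hypothesis, and that the paired test does limited harm. Much of that stands. With equal arms the test runs, its mean difference equals the unpaired one, a pairing unrelated to outcome keeps type I error at 5%, and the interval is only about 6% wider. A reader might infer that the analysis cannot be run, or that it yields no valid estimate of the FUE effect. The protocol does not support either as a general statement: the first is literally true only when the arms are unequal, and the second is untrue of the point estimate.

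Three further inferences should be resisted.

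- *A false claim of benefit from separate within-arm tests.* Suppose both arms truly improve equally and each is tested alone. The chance that FUE is significant and control is not is P(1 − P), which can never exceed 25%. It is about 9%, 13%, 23%, 20% and 10% for assumed improvements of 0.2, 0.3, 0.5, 0.8 and 1.0 SD of change. Section 9.3 does not say that within-arm tests will replace the between-group comparison, so this is a warning and not a measure of the error.
- *A wrong SD for the next trial.* With arbitrary pairs, the SD of the differences divided by √2 recovers the between-person SD. Harm follows only if someone misuses the figure.
- *Paired tests are wrong throughout.* They fit within-participant change, which is what the synopsis, the first paragraph of 9.3 and the before/after secondary objective concern.

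Nor can the point be left to an unseen SAP: the protocol itself names the test, and it conflicts with the protocol's own design.

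**Conclusion.** Wrong as written, and confined to the second paragraph of 9.3. The only stated FUE-versus-control test requires pairs that the randomisation and the bilateral treatment do not provide. The consequences are a p-value open to the choice of pairing, df halved from 22 to 11 (interval about 6% wider with no loss), and discarded participants in about 80% of trials under 20% independent loss (interval about 27% wider in expectation with pre-set pairs). These sizes assume two-sided 5%, 12 per arm and a pairing unrelated to outcome. HiSCR needs a different method whatever is decided on pairing. Section 6.4.1.1 gives a total of 20 where other sections give 24; that is a separate conflict and does not alter this conclusion.

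**What to change.** In the second paragraph of 9.3, replace sites by groups, and replace the paired t test by unpaired comparisons between groups as randomised, with the participant as the unit:

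- **IHS4, pain and lesion counts:** between-group difference with 95% CI at each follow-up visit, from ANCOVA adjusted for the Week 0 value. An unpaired t test on change would also cure the error; ANCOVA is a preference for precision.
- **HS-PGA:** a rank-based or ordinal between-group comparison.
- **HiSCR:** difference in response proportions with a CI, or Fisher's exact test.

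Keep the paired tests for before/after change within participants, but not for HiSCR. Add one sentence stating that separate tests within each arm are not evidence of a difference between groups.

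The cost is an amendment to wording. Section 6.4.1.8 already schedules the scores at Weeks 0, 6, 12 and 24, and Appendix 2 lists them at every visit without restriction by group, so no new data, visits or participants are needed. A site-level contrast should not be added under this heading: the protocol does not show that lesion counts are recorded by region, so that would be a new procedure.

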#### 6.4.1.8 HIDRADENITIS SUPPURATIVA SEVERITY ASSESSMENT

As part of standard routine care, participants will have the Hurley Stage of their HS, nodule count and abscess count documented at baseline. This is part of standard routine care to assess whether treatment is effective, and it will also allow us to calculate the hidradenitis suppurativa clinical response (HiSCR). HiSCR is defined as a  $\geq 50\%$  reduction in inflammatory lesion count (abscesses and inflammatory nodules), and no increase in abscesses or draining fistulas when compared with baseline. Participants will also have their hidradenitis suppurativa-physician's global

assessment (HS-PGA) and International Hidradenitis Suppurative Severity Score System (IHS4) score documented in follow-up visits. Pain will be assessed using the numerical scale 30 (NRS30) pain score (See Appendix 1).

These assessments will be done at week 0, week 6, week 12 and week 24.

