### c) Hidradenitis Suppurativa Physician's Global Assessment (PGA)

HS-PGA	
Clear (score = 0)	0 abscesses, 0 draining fistulas, 0 inflammatory nodules, and 0 noninflammatory nodules
Minimal (score = 1)	0 abscesses, 0 draining fistulas, 0 inflammatory nodules, and presence of noninflammatory nodules
Mild (score = 2)	0 abscesses, 0 draining fistulas, and 1–4 inflammatory nodules; or 1 abscess or draining fistula and 0 inflammatory nodules
Moderate (score = 3)	0 abscesses, 0 draining fistulas, and $\geq 5$ inflammatory nodules; or 1 abscess or draining fistula and $\geq 1$ inflammatory nodule; or 2–5 abscesses or draining fistulas and $< 10$ inflammatory nodules
Severe (score = 4)	2–5 abscesses or draining fistulas and $\geq 10$ inflammatory nodules

Very severe > 5 abscesses or draining fistulas  
(score = 5)

[figure not shown]
d) International Hidradenitis Suppurativa Severity Score System (IHS4)

IHS4 (points) =

number of nodules	× 1 +
number of abscesses	× 2 +
number of draining tunnels (fistulae/sinuses)	× 4

Mild HS: ≤ 3 points  
Moderate HS: 4–10 points  
Severe HS: ≥ 11 points

e) Numerical rating scale (NRS)

## APPENDIX 2

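### Lesion counts and IHS4 are compared by t test on unadjusted, apparently raw change; the week 0 value goes unused as a covariate, and under assumed inputs about 30% of the power is lost

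*Protocol*

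**What the plan says.** Protocol section 9.3 has two sentences on method. On counts, where the test named is again the paired t test: "Abscess and nodule counts will be recorded and then compared at the study visits up to week 24. This will be done using the paired". On scores: "Paired t test will also be used to compare changes in HS-PGA, IHS4 and HiSCR scores between the treated and control sites". The synopsis has the same test: a paired t "test to assess change in Hurley stage, Hidradenitis Suppurative-Physician's Global assessment score, numerical pain score, IHS4 score, HiSCR score".

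Neither place names a transformation, a count model or a baseline covariate.

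Other parts of the protocol describe what is being tested:
- Appendix 1 defines IHS4 as nodules ×1 plus abscesses ×2 plus draining tunnels ×4, with no upper limit. HS-PGA is six ordered grades, 0 to 5, cut from lesion counts.
- Section 6.4.1.8 defines HiSCR as at least a 50% "reduction in inflammatory lesion count (abscesses and inflammatory nodules), and no increase in abscesses or draining fistulas when compared with baseline". It schedules the assessments at weeks 0, 6, 12 and 24, so a baseline value is collected.
- Section 7.2 limits entry by Hurley stage (1 to 2A), with no minimum or cap on lesion count or IHS4.
- Sections 9.1 and 9.2 set 12 participants per group as a pilot meant to inform later sample sizes, and mention 20% loss to follow-up.

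**The concern.** A change score subtracts the whole baseline value. When baseline and follow-up are only moderately correlated, that adds noise, which regression on the baseline would remove.

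Raw change also weights participants by how many lesions they start with. Going from 20 to 10 counts as 10 points and going from 2 to 1 as 1 point, although both are the same 50% reduction that the protocol's response criterion recognises. With 12 per group and no cap on baseline count, a few high-count participants can dominate the variance.

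Two things are at stake: power to see an effect, and the quality of the variance estimate that the pilot is meant to supply to a later trial. The false-positive rate is not at stake.

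**Working it through.** **The plan's own figure.** The 24 participants come with no alpha, power, effect size or SD, so there is no calculation to reproduce. Everything below rests on assumed inputs.

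**Inputs from the protocol.** 12 per group, allocated 1:1 by participant. With 20% loss, 12 × 0.8 = 9.6, taken as 10 per group.

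**Assumed inputs.** Two-sided alpha 0.05. Poisson counts with lognormal spread between participants: mean baseline count 4, 6 or 10; CV of the underlying rate 0.4 to 1.5; within-participant log-SD 0, 0.3 or 0.6. Follow-up/baseline rate ratios, FUE against control: 0.4 v 0.9, 0.4 v 0.8, 0.5 v 1.0. The groups are compared as independent, because participants are randomised separately.

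**Measure.** Relative loss = 1 − (power of t test on raw change) / (power of comparator). Example with n = 12, mean 6, CV 0.8, ratios 0.4 v 0.9, log-SD 0.3: 46% for raw change against 65% for log ANCOVA, so 1 − 46/65 = 29%.

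**Counts, all scenarios.** Against log ANCOVA the median relative loss is 31% (12% to 61%). In absolute terms the median is 14 points (6 to 35).

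| CV | loss v log ANCOVA, median (range) | v raw ANCOVA, median | v t test on log change, median |
|---|---|---|---|
| 0.4 | 28% (15–43) | 26% | 19% |
| 0.6 | 27% (12–43) | 24% | 23% |
| 0.8 | 30% (12–45) | 24% | 27% |
| 1.0 | 33% (13–47) | 24% | 31% |
| 1.5 | 41% (19–61) | 28% | 41% |

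**Where the loss comes from.** Take raw-change power as 1 and use the medians at CV 0.8. Raw ANCOVA is 1/0.76 = 1.32 and log ANCOVA 1/0.70 = 1.43, so the baseline covariate alone supplies 0.32/0.43, about three quarters of the gain. At CV 1.5 the same sum is 0.39/0.69, a little over half. A separate run with 12 per group gave power 0.18–0.41 for raw change, 0.37–0.70 for raw ANCOVA and 0.47–0.69 for log ANCOVA, the log scale adding 0 to 10 points over raw ANCOVA. The two remedies overlap, so the split depends on their order: the last column shows that at wide spread the log scale alone recovers as much or more.

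**IHS4, built from the Appendix 1 weights (ratios 0.4 v 0.9).** Power is 26–45% on raw change against 40–64% for log ANCOVA, a relative loss of about 27–38%. For one setting with 12 per group the powers are 0.405 (raw change), 0.543 (raw ANCOVA) and 0.581 (log ANCOVA). The baseline covariate then accounts for 0.138 of the 0.176 gained.

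**Type I error.** The raw-change t test rejects in about 4–5% of null trials. Log ANCOVA on IHS4 rejects in about 5%.

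**Influence and variance.** The three most extreme of 24 participants carry a median 55–68% of the within-group sum of squares of raw change, against 47% for normal data. In a further run with heavier visit-to-visit variation, the 90th/10th percentile ratio of the pilot's estimated variance was 3.6–6.7 for raw change and 2.1–2.3 for log change. Required sample size scales with that variance.

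**The case against.** The strongest reply has four parts.

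1. *The study is a pilot with no power target, so lost power matters little.* This stands in part and lowers the weight of the point. It does not answer the variance argument, since sections 9.1 and 9.2 give later sample sizing as the pilot's purpose.

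2. *Raw is inferred, and transformations or covariates may sit in a separate analysis plan.* It is true that section 9.3 says only changes. But the protocol names the test itself, twice, and a t test on changes leaves no place for a covariate.

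3. *The counts sentence reads as a within-participant comparison across visits, where pairing is legitimate.* That reading is fair, and section 6.2 has a before-and-after objective. For that comparison the scale costs only about 0–23% of the power. The larger loss applies to the between-group comparison, after it is made unpaired.

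4. *A 50% responder threshold does not prove that the effect is a constant ratio.* Correct. The simulations assume a proportional effect. The criterion shows only that the protocol values proportional change.

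A reader might also infer more than the protocol supports:
- That half the power is lost. Heavier assumed inputs (visit CV 0.6, ratios 0.8 v 0.3) do give 0.16–0.23 against 0.42–0.56. But the protocol states no spread or effect, and across the wider grid a loss of 45% or more occurred in 1.4% of scenarios with CV up to 1.0 and 20% at CV 1.5.
- That a few participants decide the result. They strongly influence the variance; reversal of a result was not shown.
- That the t test on HS-PGA wastes power. It had 28–37% against 25–36% for a rank test on change, with type I error about 5%.

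**Conclusion.** The point holds for abscess-and-nodule counts and IHS4. As written, section 9.3 makes no use of the week 0 value as a covariate and is most naturally read as averaging raw points on skewed counts. For an unpaired comparison of the two groups this costs typically about 30% of the power in relative terms (about 12% to 61%), mostly through the missing baseline adjustment and to a smaller extent through the scale.

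The size rests on assumed spread, visit-to-visit variation and a proportional effect. The direction does not depend on the choice among them: raw change had less power than log ANCOVA in every scenario tried. Type I error is unaffected, so no re-randomisation p-value is needed. For HS-PGA the matter is one of interpretation only.

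This is a modest improvement, worth making because the same sentences need rewriting anyway: they apply a paired test to separately randomised groups and a t test to the yes/no HiSCR.

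**What to change.** In section 9.3 and the synopsis:
- Compare the groups on abscess-and-nodule count and on IHS4 by ANCOVA of log(1+score) with log(1+baseline) as covariate.
- Name the week 0 value as the baseline, since Appendix 2 schedules the scores at both screening and Visit 1.
- Report the FUE/control ratio with a 95% CI, and keep raw values descriptively.
- Optionally, add an ordinal or rank analysis of HS-PGA for interpretation. It brings no gain in power.

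The cost is wording: no extra participants, visits or data. There are two downsides. Results read as percent reduction rather than points. The +1 offset also pulls the ratio towards 1 at low counts: 20 to 10 becomes 11/21 = 0.52, but 2 to 1 becomes 2/3 = 0.67 instead of 0.50.
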